Patients with signs and symptoms of nephritis, in the absence of an identified alternate etiology, should be treated according to the guidelines in [Table 12](#).

Appendix 9

Risks Associated with Atezolizumab and Guidelines for Management of Adverse Events Associated with Atezolizumab (cont.)

Table 12 Management Guidelines for Renal Events

Event	Management
Renal event, Grade 1	
 • Continue atezolizumab. • Monitor kidney function, including creatinine, closely until values resolve to within normal limits or to baseline values.
Renal event, Grade 2	
 • Withhold atezolizumab for up to 12 weeks after event onset.^a • Refer patient to renal specialist. • Initiate treatment with corticosteroids equivalent to 1–2 mg/kg/day oral prednisone. • If event resolves to Grade 1 or better, resume atezolizumab.^b • If event does not resolve to Grade 1 or better while withholding atezolizumab, permanently discontinue atezolizumab and contact Medical Monitor.^c
Renal event, Grade 3 or 4	
 • Permanently discontinue atezolizumab and contact Medical Monitor. • Refer patient to renal specialist and consider renal biopsy. • Initiate treatment with corticosteroids equivalent to 1–2 mg/kg/day oral prednisone. • If event does not improve within 48 hours after initiating corticosteroids, consider adding an immunosuppressive agent. • If event resolves to Grade 1 or better, taper corticosteroids over ≥ 1 month.

^a Atezolizumab may be withheld for a longer period of time (i.e., > 12 weeks after event onset) to allow for corticosteroids (if initiated) to be reduced to the equivalent of ≤ 10 mg/day oral prednisone. The acceptable length of the extended period of time must be agreed upon by the investigator and the Medical Monitor.

^b If corticosteroids have been initiated, they must be tapered over ≥ 1 month to the equivalent of ≤ 10 mg/day oral prednisone before atezolizumab can be resumed.

^c Resumption of atezolizumab may be considered in patients who are deriving benefit and have fully recovered from the immune-mediated event. Patients can be re-challenged with atezolizumab only after approval has been documented by both the investigator (or an appropriate delegate) and the Medical Monitor.

Appendix 9

Risks Associated with Atezolizumab and Guidelines for Management of Adverse Events Associated with Atezolizumab (cont.)

IMMUNE-MEDIATED MYOSITIS

Immune-mediated myositis has been associated with the administration of atezolizumab. Myositis or inflammatory myopathies are a group of disorders sharing the common feature of inflammatory muscle injury; dermatomyositis and polymyositis are among the most common disorders. Initial diagnosis is based on clinical (muscle weakness, muscle pain, skin rash in dermatomyositis), biochemical (serum creatine kinase increase), and imaging (electromyography/MRI) features, and is confirmed with a muscle biopsy.

Patients with signs and symptoms of myositis, in the absence of an identified alternate etiology, should be treated according to the guidelines in [Table 13](#).

Appendix 9

Risks Associated with Atezolizumab and Guidelines for Management of Adverse Events Associated with Atezolizumab (cont.)

Table 13 Management Guidelines for Immune-Related Myositis

Event	Management
Immune-mediated myositis, Grade 1	
 • Continue atezolizumab. • Refer patient to rheumatologist or neurologist. • Initiate treatment as per institutional guidelines.
Immune-mediated myositis, Grade 2	
 • Withhold atezolizumab for up to 12 weeks after event onset^a and contact Medical Monitor. • Refer patient to rheumatologist or neurologist. • Initiate treatment as per institutional guidelines. • Consider treatment with corticosteroids equivalent to 1–2 mg/kg/day IV methylprednisolone and convert to 1–2 mg/kg/day oral prednisone or equivalent upon improvement. • If corticosteroids are initiated and event does not improve within 48 hours after initiating corticosteroids, consider adding an immunosuppressive agent. • If event resolves to Grade 1 or better, resume atezolizumab.^b • If event does not resolve to Grade 1 or better while withholding atezolizumab, permanently discontinue atezolizumab and contact Medical Monitor.^c

^a Atezolizumab may be withheld for a longer period of time (i.e., >12 weeks after event onset) to allow for corticosteroids (if initiated) to be reduced to the equivalent of ≤ 10 mg/day oral prednisone. The acceptable length of the extended period of time must be agreed upon by the investigator and the Medical Monitor.

^b If corticosteroids have been initiated, they must be tapered over ≥ 1 month to the equivalent of ≤ 10 mg/day oral prednisone before atezolizumab can be resumed.

^c Resumption of atezolizumab may be considered in patients who are deriving benefit and have fully recovered from the immune-mediated event. Patients can be re-challenged with atezolizumab only after approval has been documented by both the investigator (or an appropriate delegate) and the Medical Monitor.

Appendix 9

Risks Associated with Atezolizumab and Guidelines for Management of Adverse Events Associated with Atezolizumab (cont.)

Table 13 Management Guidelines for Immune-Mediated Myositis (cont.)

Immune-mediated myositis, Grade 3	
 • Withhold atezolizumab for up to 12 weeks after event onset^a and contact Medical Monitor. • Refer patient to rheumatologist or neurologist. • Initiate treatment as per institutional guidelines. • Respiratory support may be required in more severe cases. • Initiate treatment with corticosteroids equivalent to 1–2 mg/kg/day IV methylprednisolone, or higher-dose bolus if patient is severely compromised (e.g., cardiac or respiratory symptoms, dysphagia, or weakness that severely limits mobility); convert to 1–2 mg/kg/day oral prednisone or equivalent upon improvement. • If event does not improve within 48 hours after initiating corticosteroids, consider adding an immunosuppressive agent. • If event resolves to Grade 1 or better, resume atezolizumab.^b • If event does not resolve to Grade 1 or better while withholding atezolizumab, permanently discontinue atezolizumab and contact Medical Monitor.^c • For recurrent events, treat as a Grade 4 event.
Immune-mediated myositis, Grade 4	
 • Permanently discontinue atezolizumab and contact Medical Monitor.^c • Refer patient to rheumatologist or neurologist. • Initiate treatment as per institutional guidelines. • Respiratory support may be required in more severe cases. • Initiate treatment with corticosteroids equivalent to 1–2 mg/kg/day IV methylprednisolone, or higher-dose bolus if patient is severely compromised (e.g., cardiac or respiratory symptoms, dysphagia, or weakness that severely limits mobility); convert to 1–2 mg/kg/day oral prednisone or equivalent upon improvement. • If event does not improve within 48 hours after initiating corticosteroids, consider adding an immunosuppressive agent. • If event resolves to Grade 1 or better, taper corticosteroids over ≥ 1 month.

^a Atezolizumab may be withheld for a longer period of time (i.e., > 12 weeks after event onset) to allow for corticosteroids (if initiated) to be reduced to the equivalent of ≤ 10 mg/day oral prednisone. The acceptable length of the extended period of time must be agreed upon by the investigator and the Medical Monitor.

^b If corticosteroids have been initiated, they must be tapered over ≥ 1 month to the equivalent of ≤ 10 mg/day oral prednisone before atezolizumab can be resumed.

^c Resumption of atezolizumab may be considered in patients who are deriving benefit and have fully recovered from the immune-mediated event. Patients can be re-challenged with atezolizumab only after approval has been documented by both the investigator (or an appropriate delegate) and the Medical Monitor.

Appendix 9

Risks Associated with Atezolizumab and Guidelines for Management of Adverse Events Associated with Atezolizumab (cont.)

HEMOPHAGOCYTIC LYMPHOHISTIOCYTOSIS AND MACROPHAGE ACTIVATION SYNDROME

Immune-mediated reactions may involve any organ system and may lead to hemophagocytic lymphohistiocytosis (HLH) and macrophage activation syndrome (MAS), which are considered to be potential risks for atezolizumab.

Patients with suspected HLH should be diagnosed according to published criteria by McClain and Eckstein (2014). A patient should be classified as having HLH if five of the following eight criteria are met:

- Fever $\geq 38.5^{\circ}\text{C}$
- Splenomegaly
- Peripheral blood cytopenia consisting of at least two of the following:
 - Hemoglobin $< 90 \text{ g/L}$ (9 g/dL) ($< 100 \text{ g/L}$ [10 g/dL] for infants < 4 weeks old)
 - Platelet count $< 100 \times 10^9/\text{L}$ ($100,000/\mu\text{L}$)
 - ANC $< 1.0 \times 10^9/\text{L}$ ($1000/\mu\text{L}$)
- Fasting triglycerides $> 2.992 \text{ mmol/L}$ (265 mg/dL) and/or fibrinogen $< 1.5 \text{ g/L}$ (150 mg/dL)
- Hemophagocytosis in bone marrow, spleen, lymph node, or liver
- Low or absent natural killer cell activity
- Ferritin $> 500 \text{ mg/L}$ (500 ng/mL)
- Soluble interleukin 2 (IL-2) receptor (soluble CD25) elevated ≥ 2 standard deviations above age-adjusted laboratory-specific norms

Patients with suspected MAS should be diagnosed according to published criteria for systemic juvenile idiopathic arthritis by Ravelli et al. (2016). A febrile patient should be classified as having MAS if the following criteria are met:

- Ferritin $> 684 \text{ mg/L}$ (684 ng/mL)
- At least two of the following:
 - Platelet count $\leq 181 \times 10^9/\text{L}$ ($181,000/\mu\text{L}$)
 - AST $\geq 48 \text{ U/L}$
 - Triglycerides $> 1.761 \text{ mmol/L}$ (156 mg/dL)
 - Fibrinogen $\leq 3.6 \text{ g/L}$ (360 mg/dL)

Patients with suspected HLH or MAS should be treated according to the guidelines in [Table 14](#).

Appendix 9

Risks Associated with Atezolizumab and Guidelines for Management of Adverse Events Associated with Atezolizumab (cont.)

Table 14 Management Guidelines for Suspected Hemophagocytic Lymphohistiocytosis or Macrophage Activation Syndrome

Event	Management
Suspected HLH or MAS	
 • Permanently discontinue atezolizumab and contact Medical Monitor. • Consider patient referral to hematologist. • Initiate supportive care, including intensive care monitoring if indicated per institutional guidelines. • Consider initiation of IV corticosteroids and/or an immunosuppressive agent. • If event does not improve within 48 hours after initiating corticosteroids, consider adding an immunosuppressive agent. • If event resolves to Grade 1 or better, taper corticosteroids over ≥ 1 month.

HLH=hemophagocytic lymphohistiocytosis; MAS=macrophage activation syndrome.

REFERENCES

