3.1.2 Safety Evaluation Phase

3.1.2.1 Dose-Limiting Toxicity Assessment

The first 6 patients enrolled in the safety cohort will be eligible for DLT assessment. The DLT assessment window for the safety cohort is 56 days from the first dose of Hu5F9-G4.

All patients who experience a DLT during the DLT assessment window will be considered evaluable for safety evaluation decisions.

Patients who withdraw from study treatment (atezolizumab plus Hu5F9-G4) for any reason other than a DLT during this assessment window will not be considered evaluable for safety evaluation decisions and will be replaced. The total number of enrolled patients in this study will be capped at 21 patients. If patients are replaced prior to DLT assessment, discontinued patients will be counted toward the total limit of 21 patients.

During the DLT evaluation window, patients will not be allowed to make up missed doses; patients will resume dosing at their next scheduled dose. Patients who are unable to receive the next scheduled dose of Hu5F9-G4 or atezolizumab as a result of study treatment-related adverse events will be considered to have met the DLT criteria.

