- Grade 3 tumor lysis syndrome or electrolyte disturbances (hyperkalemia, hypophosphatemia, hyperuricemia, etc.) that resolve to Grade ≤ 2 or baseline value within 7 days
- Grade 3 or 4 lymphopenia or leukopenia
- Any Grade 3 autoimmune toxicity that clinically resolves to Grade ≤ 2 within 7 days of initiating therapy
- Grade 3 diarrhea or skin toxicity that resolves to Grade 1 or better in <7 days after medical management (e.g., immunosuppressant treatment) has been initiated
- Other single laboratory values out of normal range that have no clinical correlate and resolve to Grade ≤ 2 or to baseline within 7 days with adequate medical management
- Tumor flare phenomenon defined as local pain, irritation, or rash localized at sites

Appendix 8

Overall Guidelines for Management of Patients Who Experience Adverse Events (cont.)

Patients who are deemed to require further dose reductions <20 mg/kg of Hu5F9-G4 should be discontinued from study treatment with Hu5F9-G4.

TREATMENT INTERRUPTION

Atezolizumab treatment may be temporarily suspended in patients experiencing toxicity considered to be related to study treatment. If corticosteroids are initiated for treatment of the toxicity, they must be tapered over ≥ 1 month to the equivalent of ≤ 10 mg/day oral prednisone before atezolizumab can be resumed. If atezolizumab is withheld for > 12 weeks after event onset, the patient will be discontinued from atezolizumab. However, atezolizumab may be withheld for > 12 weeks to allow for patients to taper off corticosteroids prior to resuming treatment. Atezolizumab can be resumed after being withheld for > 12 weeks if the Medical Monitor agrees that the patient is likely to derive clinical benefit. Atezolizumab treatment may be suspended for reasons other than toxicity (e.g., surgical procedures) with Medical Monitor approval. The investigator and the Medical Monitor will determine the acceptable length of treatment interruption.

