IRR, Grade 1	
Follow guidelines for atezolizumab in Appendix 9.For anaphylaxis precautions, see Appendix 7.
IRR, Grade 2	
Follow guidelines for atezolizumab in Appendix 9.For anaphylaxis precautions, see Appendix 7.For Hu5F9-G4:
Stop the Hu5F9-G4 infusion, begin an IV infusion of normal saline, and treat the patient with diphenhydramine 50 mg IV or equivalent and/or 500 to 750 mg oral paracetamol/acetaminophen.Remain at bedside and monitor patient until resolution of symptoms.Corticosteroid therapy may also be administered at the discretion of the investigator.If the infusion is interrupted, wait until symptoms resolve, then restart the infusion at 50% of the original infusion rate when symptoms resolve.If symptoms recur, then stop infusion and disconnect the patient from the infusion apparatus; no further Hu5F9-G4 will be administered at that visit. The amount of study drug infused must be recorded on the electronic Case Report Form.Patients who experience an infusion reaction of Grade 2 during the 4-hour post-infusion observation period that does not resolve during that time should be observed for 24 hours or until the adverse event resolves, with vital sign measurements every 4 hours and additional evaluations as medically indicated for the management of the adverse event.

IRR=infusion-related reaction.

Appendix 8
Overall Guidelines for Management of Patients Who Experience Adverse Events (cont.)

Table 1 Guidelines for Management of Patients Who Experience Adverse Events Associated with Hu5F9-G4 (cont.)

Event	Action to Be Taken
IRRs and anaphylaxis (cont.)	

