- ^b If corticosteroids have been initiated, they must be tapered over ≥ 1 month to the equivalent of ≤ 10 mg/day oral prednisone before atezolizumab can be resumed.
- ^c Resumption of atezolizumab may be considered in patients who are deriving benefit and have fully recovered from the immune-mediated event. Patients can be re-challenged with atezolizumab only after approval has been documented by both the investigator (or an appropriate delegate) and the Medical Monitor.

Appendix 9

Risks Associated with Atezolizumab and Guidelines for Management of Adverse Events Associated with Atezolizumab (cont.)

HEPATIC EVENTS

Immune-mediated hepatitis has been associated with the administration of atezolizumab. Eligible patients must have adequate liver function, as manifested by measurements of total bilirubin and hepatic transaminases, and liver function will be monitored throughout study treatment. Management guidelines for hepatic events are provided in [Table 2](#).

Patients with right upper-quadrant abdominal pain and/or unexplained nausea or vomiting should have liver function tests (LFTs) performed immediately and reviewed before administration of the next dose of study drug.

For patients with elevated LFTs, concurrent medication, viral hepatitis, and toxic or neoplastic etiologies should be considered and addressed, as appropriate.

Table 2 Management Guidelines for Hepatic Events

Event	Management
Hepatic event, Grade 1	
Continue atezolizumab.Monitor LFTs until values resolve to within normal limits or to baseline values.
Hepatic event, Grade 2	
All events:
 
Monitor LFTs more frequently until return to baseline values. 
Events of > 5 days' duration:
 
Withhold atezolizumab for up to 12 weeks after event onset.^aInitiate treatment with corticosteroids equivalent to 1–2 mg/kg/day oral prednisone.If event resolves to Grade 1 or better, resume atezolizumab.^bIf event does not resolve to Grade 1 or better while withholding atezolizumab, permanently discontinue atezolizumab and contact Medical Monitor.^c

LFT = liver function test.

^a Atezolizumab may be withheld for a longer period of time (i.e., >12 weeks after event onset) to allow for corticosteroids (if initiated) to be reduced to the equivalent of ≤ 10 mg/day oral prednisone. The acceptable length of the extended period of time must be agreed upon by the investigator and the Medical Monitor.

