
Grade 2^a
 
Fever^b with hypotension not requiring vasopressors
 
and/or
 
Hypoxia requiring low-flow oxygen^d by nasal cannula or blow-by
	
 • Immediately interrupt infusion. • Upon symptom resolution, wait for 30 minutes and then restart infusion at half the rate being given at the time of event onset. • If symptoms recur, discontinue infusion of this dose. • Administer symptomatic treatment.^c • For hypotension, administer IV fluid bolus as needed. • Monitor cardiopulmonary and other organ function closely (in the ICU, if appropriate). Administer IV fluids as clinically indicated, and manage constitutional symptoms and organ toxicities as per institutional practice. • Rule out other inflammatory conditions that can mimic CRS (e.g., sepsis). If no improvement within 24 hours, initiate workup and assess for signs and symptoms of HLH or MAS as described in this appendix. • Consider IV corticosteroids (e.g., methylprednisolone 2 mg/kg/day or dexamethasone 10 mg every 6 hours). • Consider anti-cytokine therapy.^e • Consider hospitalization until complete resolution of symptoms. If no improvement within 24 hours, manage as per Grade 3, that is, hospitalize patient (monitoring in the ICU is recommended), permanently discontinue atezolizumab, and contact Medical Monitor. • If symptoms resolve to Grade 1 or better for 3 consecutive days, the next dose of atezolizumab may be administered. • For subsequent infusions, consider administration of oral premedication with antihistamines, anti-pyretics, and/or analgesics and monitor closely for IRRs and/or CRS. • If symptoms do not resolve to Grade 1 or better for 3 consecutive days, contact Medical Monitor.
--	--

Appendix 9

Risks Associated with Atezolizumab and Guidelines for Management of Adverse Events Associated with Atezolizumab (cont.)

Table 7 Management Guidelines for Infusion-Related Reactions and Cytokine-Release Syndrome (cont.)

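### Appendices 8 and 9 give conflicting conditions for re-dosing atezolizumab after a steroid-treated Grade 2 infusion reaction, so the same event at the Day 22 or Day 36 dose may or may not be a DLT

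*Combined protocol and SAP*

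**What the plan says.** **Appendix 8, Treatment Interruption.** Atezolizumab may be suspended for toxicity considered related to study treatment. The condition for resuming it is: "If corticosteroids are initiated for treatment of the toxicity, they must be tapered over ≥ 1 month", down to no more than 10 mg/day of oral prednisone or equivalent. The sentence is not limited by type of event.

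**Appendix 8 Table 1, IRR Grade 2.** The row first sends the reader to Appendix 9 for atezolizumab. Under Hu5F9-G4 it adds: "Corticosteroid therapy may also be administered at the discretion of the investigator".

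**Appendix 9 Table 7, Grade 2 IRR/CRS.** The investigator is told to consider IV corticosteroids. The re-dosing condition is: "If symptoms resolve to Grade 1 or better for 3 consecutive days, the next dose of atezolizumab may be administered". If there is no improvement within 24 hours, the event is managed as Grade 3 and atezolizumab is permanently discontinued. The Table 7 footnotes contain no taper condition.

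**Section 3.1.2.1.** "Patients who are unable to receive the next scheduled dose of Hu5F9-G4 or atezolizumab as a result of study treatment-related adverse events" are considered to have met the DLT criteria. During the window, "patients will not be allowed to make up missed doses". The window is 56 days from the first Hu5F9-G4 dose.

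**Section 3.1.2.3.** By grade, infusion-related toxicity is a DLT only from Grade 3 upward.

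**Section 3.1.2.2.** Two or more DLTs in 6 lead to a de-escalation cohort. One or none leads to an expansion cohort of 15.

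**The concern.** A Grade 2 infusion reaction is below the grade threshold for a DLT, so it can count only through the missed-dose rule. Whether a dose is missed depends on which re-dosing condition the site applies, and for a reaction treated with corticosteroids the two appendices give different answers. Two patients with identical events at different sites could be classified differently.

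The DLT count in 6 patients decides whether Hu5F9-G4 maintenance stays at 30 mg/kg or goes to the 15 mg/kg de-escalation cohort, and whether the expansion has 15 or 9 patients. With so small a denominator, one reclassified patient can change the decision. Apart from the count, sites hold contradictory instructions on when a patient may be re-dosed.

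**Working it through.** **1. The plan's own rule.** 1/6 = 16.7%, which is below 33% (expand). 2/6 = 33.3%, which is at least 33% (de-escalate). The window is 2 × 28 = 56 days. These agree with the text.

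**2. Atezolizumab days** (Section 3.1.1). Cycle 1 Day 22 is study Day 22. Cycle 2 Days 8 and 22 are 28 + 8 = Day 36 and 28 + 22 = Day 50. Cycle 3 Day 8 is 56 + 8 = Day 64. Successive doses are 14 days apart.

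**3. Earliest re-dosing day under each text.** Assumptions: corticosteroids start on the day of the reaction, symptoms settle within 1 day, and 1 month is 28 to 31 days.
- Table 7: reaction day + 1 + 3.
- Appendix 8: reaction day + 28 to 31.

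| Reaction at | Next dose | Table 7 allows from | Appendix 8 allows from | Next dose in window? | DLT status differs? |
|---|---|---|---|---|---|
| Day 22 | Day 36 | Day 26 | Day 50–53 | yes | yes |
| Day 36 | Day 50 | Day 40 | Day 64–67 | yes | yes |
| Day 50 | Day 64 | Day 54 | Day 78–81 | no | no |

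The ±3-day visit allowance in Appendix 2 does not change the last column. The Day 36 dose could be given as late as Day 39, against Day 50 at the earliest under Appendix 8. The Day 50 dose could be given as late as Day 53, against Day 64. The Day 64 dose could come no earlier than Day 61, still after Day 56.

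**4. Effect on the 2-of-6 rule.** The documents give neither rate needed here, so both are assumed. Let *b* be the chance that a patient has some other DLT, and *q* the chance of a reaction of the kind in rows 1 and 2, independent of each other. If the reactions count, p = 1 − (1 − b)(1 − q). If they do not, p = b. Then

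P(2 or more of 6) = 1 − (1 − p)^6 − 6p(1 − p)^5.

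With b = 10%:
- not counted, p = 0.100: 1 − 0.531 − 0.354 = 11.4%
- q = 2%, p = 0.118: 1 − 0.471 − 0.378 = 15.1%
- q = 5%, p = 0.145: 1 − 0.391 − 0.398 = 21.2%
- q = 10%, p = 0.190: 1 − 0.282 − 0.397 = 32.0%

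At other values of b, the same formula gives:

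| b | not counted | q = 5% | q = 10% |
|---|---|---|---|
| 5% | 3.3% | 10.9% | 21.2% |
| 20% | 34.5% | 44.2% | 53.6% |

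**The case against.** The best defence is that Table 7 is meant to govern. Appendix 8 Table 1 itself refers Grade 2 IRRs to Appendix 9, and Table 7 gives a condition specific to the event. The Appendix 8 sentence also opens with suspension of treatment, whereas Table 7 Grade 2 interrupts an infusion and does not withhold the drug for weeks. In Appendix 9 the taper footnote is attached to the withhold-and-resume entries of the organ-toxicity tables, so its absence from Table 7 could be deliberate. A month-long taper also fits poorly with a single steroid dose.

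This may well be the intent, but the text does not say so. The cross-reference waives nothing, the taper sentence is mandatory and covers toxicity related to study treatment in general, and Section 5.1 sends sites to both appendices for interruption criteria. Nor does the conflict depend on one small dose, because the Table 7 examples are repeated daily or 6-hourly regimens.

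The defence is right that the event is narrow. It must be Grade 2 as Table 7 defines it (fever with hypotension or with hypoxia needing low-flow oxygen), occur at the first or second atezolizumab dose, be treated with optional corticosteroids, and improve within 24 hours. Without that improvement, Table 7 leads to permanent discontinuation, and the next dose is missed under either text. An event reported as CTCAE Grade 3 or higher is a DLT by grade. Section 5.1.2 places Hu5F9-G4 reactions mainly at the first few doses, which come before Day 22. High event rates are therefore hard to justify from these documents.

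**Conclusion.** The contradiction is real and sits in operative text. For a steroid-treated Grade 2 IRR/CRS at the Day 22 or Day 36 dose that improves within 24 hours, Appendix 8 makes the patient miss the next in-window dose and hence meet the DLT criterion, while Table 7 does not. One such patient is enough to turn 1/6 into 2/6. The probabilities (11% rising to about 15%, 21% or 32%) rest on assumed rates and show only direction and rough scale. The calendar result needs no event rate.

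A reader might infer three stronger points that the documents do not support:
- **That a Day 22 reaction necessarily costs both the Day 36 and Day 50 doses.** With a 28-day month, Appendix 8 allows dosing on Day 50. With 30 or 31 days it allows Day 52 or 53, which the ±3-day allowance can reach. Missing Day 36 alone triggers the rule.
- **That these events also feed the expansion stopping boundaries in Table 1 of Section 3.1.2.4.** That section defines excess toxicity by the criteria in 3.1.2.3, whereas the missed-dose rule is in 3.1.2.1. Whether it carries over is unclear.
- **That every such reaction in the window is affected.** One at Day 50 does not change in-window status.

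**What to change.** 1. Reconcile Appendix 8 (Treatment Interruption and Table 1, IRR Grade 2) with Appendix 9 Table 7, so that one stated rule governs re-dosing after corticosteroids given for an IRR or CRS and appears in both appendices. Which rule that should be is a clinical decision on which this review takes no position.
2. State in Section 3.1.2.1 whether a dose missed only because of the taper requirement meets the missed-dose DLT criterion. State also whether the missed-dose rule applies to the expansion stopping boundary in Section 3.1.2.4.
3. At cohort review, list separately any DLT that arises only from the missed-dose rule, so that its effect on the 2-of-6 decision is visible.

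The cost is a few sentences in the two appendices and Section 3.1.2.1, with a matching clause in Section 3.1.2.4. No new data or patients are needed. The change should be in place before the safety cohort is reviewed.
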